Version Number	Version Date	Summary of Changes
V1.0		SAP signed off

2. General

2.1 Document Scope

This statistical analysis plan (SAP) covers the reporting of the trial progress and planned effectiveness analyses of the ComBAT trial. Analyses relating to qualitative data and further exploratory post-hoc analyses are not covered by this SAP, along with health economic analyses, which are covered by the health economics analysis plan.

2.2 Glossary

AE	Adverse Events
BA	Behavioural Activation
BADS-SF	Behavioural Activation for Depression Scale – Short Form
CAMHS	Child and Adolescent Mental Health Services
CBT	Cognitive Behavioural Therapy
CDRS-R	Children's Depression Rating Scale-Revised
CHU-9D	Child Health Utility Index
ComBAT	Community-Based Behavioural Activation Training
CRF	Case Report Form
IPT	Interpersonal Psychotherapy
ITT	Intention to Treat
MAR	Missing At Random
PHQ-9A	Patient Health Questionnaire – Modified for Adolescents
PPI	Patient-Public Involvement
PROM	Patient Reported Outcome Measure
RA	Research Assistant
RAG	Red-Amber-Green
RCADS	Revised Children's Anxiety and Depression Scale
RUQ-A	Resource Utilisation Questionnaire for Adolescents
SAE	Serious Adverse Events
SOPs	Standard Operating Procedures
UC	Usual Care
YTU	York Trials Unit

2.3 Procedural documentation

2.3.1 Standard operating procedures

The following York Trials Unit (YTU) Standard Operating Procedures (SOPs) and guidance documents will apply to the conduct and documentation of the ComBAT trial analysis.

S01	Statistical Considerations	Latest version: 6.0
SG02	Statistical and Health Economics Reporting	Latest version: 4.0
TP30	Statistical Quality Control Log	Latest version: 2.0

SG05	Using the Statistical Quality Control Log	Latest version: 1.0
------	---	---------------------

2.3.2 Associated documentation

Appropriate YTU standard forms apply. Any assumptions made during the processing and merging of data as well as for the analysis will be documented (internal document reference numbers in bracket) using an Assumptions Log (TP31). In the event of necessary changes or additions to analyses detailed here, these will be documented on an Analysis Plan Departure Log (F27). The statistical analysis will be signed off using a Primary Analysis Sign-off Form (F16) and Statistical Quality Assurance Checklist (C03).

3. Trial Summary

This section gives a summary of the ComBAT trial.

3.1 Objectives

The aim of this study is to evaluate the effectiveness of Behavioural Activation (BA) against usual care to reduce depression in young people.

3.2 Design

This study is a parallel two-arm randomised control trial (RCT), aiming to recruit 236 young people with mild to moderate depression, to compare the effectiveness of behavioural activation (BA) against usual care. The study will include an internal 9-month pilot, whereby a red-amber-green (RAG) rating will be applied to assess the capability of the RCT to recruit and retain young people at the required rate.

Nested within the study will be a phenomenological study to examine the acceptability of BA, an ethnographic study to investigate how BA has been delivered in different sites and an economic evaluation of BA's cost-effectiveness relative to usual care.

Full details of the background and design of the trial are presented in the study protocol.

3.3 Interventions

3.3.1 Behavioural activation

A bespoke, standardised BA package was developed which was inspired and informed by published literature, public and patient involvement (PPI) activities and a feasibility study.

The BA sessions with a professional will guide and support each young person to identify, schedule, complete and monitor pleasures, necessities and goals in day-to-day life that connect with what and who is important to them. These may be things that the young person has stopped doing or doing less, which they can start doing again or more. There may be things that the young person would like to do or things that the young person never thought of doing for which they need help to start. There may be things that they have been doing routinely but no longer enjoy and need to change them in some way.

The young person will keep a diary in which they will make a note of each activity that they complete. Some of these activities will be scheduled and others will be unplanned, routine or spontaneous. The young person will score enjoyment, achievement and/or connection for each activity on a 0-10 scale (0=no enjoyment/achievement/connection, 10=great enjoyment/achievement/connection). Over the course of the week, activities that score high

on enjoyment, achievement and connection are highlighted and encouraged. Activities that score low can be reduced or changed so that they become more enjoyable or rewarding.

Activities that have not been completed can be postponed, cancelled, or changed – depending on the reasons for not being completed (the young person did not consider them important, or they were too difficult or other activities took priority). A graded and stepped approach to activities will help young people overcome obstacles such as hesitation and tiredness that are to be expected with depression. Some activities may actually make young people feel worse or may be harmful, destructive or counterproductive; these need to be identified and reduced/stopped.

The BA programme is organised in 5 “modules” which can be completed in up to 8 weekly sessions of 30-40 minutes each in a blended model of professional-guided sessions and self-directed activities. A 5-module approach has been used by McCauley et al (2016a) in their published guide (pp. 12-13). The content of these 5 modules is bespoke to ComBAT.

Table 1: The Five BA modules in ComBAT.

Module	Topics covered
Module 1: Starting Up	
 • What is depression? • What is behavioural activation? • Emotional rewards or ‘positive reinforcement’ • The depression cycle. • Behavioural activation: breaking the depression cycle. • Take away activities: Activity monitoring and making the most of good feelings
Module 2: Getting Active	
 • Reviewing the weekly calendar • Understand what the PAC scores mean. Compare high vs low PAC activities and identify what makes a difference. • Introduction to the “Life Pie”: personal areas of importance and values • Turning values into activities: pleasures, necessities and goals across the life pie. • Introduction to activity scheduling • Activity monitoring
Module 3: Building Skills	
 • Building on activity review 
 ○ Identify activities with high and low PAC scores. • Activity scheduling: 
 ○ Repeat activities with high PAC scores. ○ Introduce pleasures, necessities and goals across more areas of the life pie. ○ Reduce, remove or modify activities with low PAC scores. • Activity monitoring
Module 4: Overcoming Obstacles	
 • Reviewing the weekly calendar 
 ○ Identify activities with high and low PAC scores. ○ Identify non-completed scheduled activities. ○ Identify barriers and problems. ○ Identify harmful or counterproductive activities. • Identify and manage barriers and problem solve. • Mastering activity scheduling: 
 ○ Repeat activities with high PAC scores.

	
 ○ Introduce new pleasures, necessities and goals for more areas of the life pie. ○ Reduce, remove or modify activities with low PAC scores. ○ Reduce, remove or modify harmful or counterproductive activities. ○ Introduce activities that counteract avoidance, overcome barriers and solve problems.
Module 5: Moving Forward	
 • Review weekly calendar. • Create an activities bank by looking through the previous weekly calendars. • Plan pleasures, necessities and goals to focus on in the next 4 weeks. • Create a relapse prevention plan.

3.3.2 Usual care

Usual practice for child and adolescent mental health can be widely varied and inconsistent, as we have learnt from the mapping exercise, we carried out within our feasibility study and from our experiences of completing similar NIHR-funded studies, including ASPECT (Wright, et al., 2018), I-SOCIALISE (Varley et al., 2019), CCBT (Wright et al., 2017), Young SMILES (Gellatly et al, 2019). Usual care may be no intervention, signposting to alternative sources of support, general discussion, supportive counselling, relaxation, recreation groups, guided self-help or psychological therapies including CBT and IPT.

Professionals who are involved in usual care also vary greatly from one community setting to another: from assistants and support workers (e.g. family support workers, teaching assistants, emotional literacy support workers) to professionals who are trained in counselling, low intensity interventions (e.g. psychological wellbeing practitioners) and specialist high intensity interventions (e.g. CBT therapists, family therapists). This was reflected in our mapping exercise completed within our feasibility study where we also found much variation in the frequency, and both session number and length of support offered to young people with depression across services.

3.4 Outcomes

3.4.1 Primary Outcome

- *Revised Children's Anxiety and Depression Scale-Brief Version:*
 - *Variable type:* Continuous.
 - *Range and polarity:* Each item can take a score from 0-3, and the total raw score ranges from 0-75. Raw scores are then converted to T-scores for the appropriate gender and school year. Derivation of T-scores are given in more detail in Section 5.3.1. Higher raw scores and t-scores represent higher levels of depression and anxiety.
 - *Timepoints:* The RCADS-25 was collected at baseline, 6 months post-randomisation and 12-months post-randomisation.

3.4.2 Secondary Outcomes

The secondary outcomes are:

- *Children's Depression Rating Scale-Revised (CDRS-R):*

- *Variable type:* Continuous
- *Range and polarity:* This 17-item researcher administered interview has 3 items scoring between 1-5 and 14 items between 1-7. The total score ranges between 17-113. A higher score suggests greater levels of depressive symptoms, with a score of 40 indicating diagnosable depression.
- *Follow-up:* The CDRS-R is collected at baseline, 6 months post-randomisation and 12-months post-randomisation.
- *Behavioural Activation for Depression Scale (BADS-SF):*
 - *Variable type:* Continuous
 - *Range and polarity:* Each item is scaled from 0-6, giving a total score ranging between 0-54. A higher score represents increased behavioural activation.
 - *Follow-up:* The BADS-SF is collected at baseline, 6 months post-randomisation and 12-months post-randomisation.

3.4.3 Other Collected Data

- **Screening CRF**
 - PHQ-9A:
 - items 1-9
 - supplementary items 10-13 (risk questions)
 - total raw score
 - Date of screening
 - Inclusion criteria:
 - Aged between 12-18 years of age.
 - Scored at least 65 on the RCADS Depression Subscale.
 - Scored at most 14 on the PHQ-9A and did not answer risk questions in the affirmative (if scored greater than 14 – attends a secondary eligibility assessment with clinical member of the ComBAT team).
 - Exclusion criteria:
 - Young person eligible for secondary care CAMHS
- **Screening log**
 - Young person's initials (ID given if randomised)
 - Site name
 - Site ID
 - Name of location young person referred from:
 - Child and Adolescent Mental Health Services (CAMHS) name
 - Charity/Service name
 - School name
 - Referring professional
 - Research assistant
 - Date expression of interest received
 - Date of screening
 - RCADS Depression subscale score (as determined by screening CRF)
 - PHQ-9A score (as determined by screening CRF)
 - Young person eligible
 - Clinician follow-up call
 - Reason for screen failure/reason for ineligibility
 - Young person contacted for consent
 - Young person consented
 - Reason for non-consent
 - Additional notes

- **Baseline CRF**
 - Participant ID
 - Date completed
 - Date of birth
 - Gender
 - Ethnicity
 - Religion
 - Current living status
 - Living with parents, friends, alone, etc.
 - Number of people living in the same household
 - Number of people under 18 in the same household
 - Current education status
 - In education
 - Type of education
 - Employment status
 - Preference of support delivery
- **Therapist Demographic Information**
 - Therapist initials
 - Role (e.g. Child wellbeing practitioner, Nurse, Counsellor)
 - Grade
 - Organisation
 - Age (Grouped)
 - Gender
 - Time working with young people
 - Approaches used when supporting young people
- **Session record (behavioural activation)**
 - Participant ID
 - Date completed
 - Location of session (online, telephone, in person)
 - Professional's name
 - Session recorded
 - Adverse events
 - Anyone else present (parent, sibling etc.)
 - Type of session (assessment, intervention, or review)
 - Strategies used during the session
 - Time spent preparing the session (mins)
 - Length of session (mins)
 - Time spent on administration after the session (mins)
- **Session record (usual care)**
 - Participant ID
 - Date completed
 - Location of session (online, telephone, in person)
 - Professional's name
 - Session recorded
 - Adverse events
 - Anyone else present (parent, sibling etc.)
 - Approach and support offered during the session
 - Strategies covered during the session
 - Time spent preparing the session (mins)
 - Length of session (mins)

- Time spent on administration after the session (mins)
- **Month 6 CRF**
 - Participant ID
 - Date completed
 - Aspects of care questionnaire (8-items)
- **Month 12 CRF**
 - Participant ID
 - Date completed
 - Aspects of care questionnaire (8-items)
- **Fidelity assessment**
 - Professional's name
 - Name of person assessing fidelity
 - Participant ID
 - Date of session
 - Session number
 - Professional's ability to deliver intervention (behavioural activation sessions only, 1-Limited, 2-Sufficient, 3-Excellent)
- **Change of Status**
 - Participant ID
 - Date completed
 - Date of birth
 - Pre-randomisation withdrawal
 - Post-randomisation withdrawal (treatment only, follow-up only, full withdrawal)
 - Reason for change in status
 - Date of death (if applicable)
 - Further information of change in status
 - Researchers name
 - Researchers signature
- **Unblinding**
 - Participant ID
 - Date of unblinding
 - Source of unblinding
 - Reason for unblinding
 - Method of unblinding
 - Additional details
- **Adverse events**
 - Participant ID
 - Date event reported
 - Event type (non-serious or serious AE)
 - Event reported by
 - Event reported to
 - Time point of adverse event
 - Date of onset of event
 - Description of event and how it was reported
 - Outcome of event (recovered/still ongoing)
 - Date recovered (if applicable)
 - Additional comments
 - Name of person reporting AE
 - Date report completed
 - Name of ComBAT team member reviewing the AE

- Date report reviewed
- **Serious adverse events**
 - Participant ID
 - Date event reported
 - Event reported by
 - Event reported to
 - Time point of adverse event
 - Date of onset of event
 - Description of event and how it was reported
 - Classification of SAE
 - CI Assessment-Expected SAE
 - Relationship to support received
 - Outcome of event (fully recovered / partially recovered / still ongoing / died)
 - Date fully recovered (if applicable)
 - Date partially recovered (if applicable)
 - Date of death (if applicable)
 - Name of person reporting SAE
 - Date report completed
 - Name of ComBAT team member reviewing the SAE
 - Date report reviewed
- **Adverse event follow-up**
 - Participant ID
 - Date initial event reported
 - Date of event follow-up
 - Event follow-up reported by
 - Event follow-up reported to
 - Time point of event follow-up
 - Date of onset of event
 - Outcome of event (fully recovered / partially recovered / still ongoing)
 - Additional actions since initial report
 - Date recovered (if applicable)
 - Further comments
 - Name of person reporting AE
 - Date report completed
 - Name of ComBAT team member reviewing the AE
 - Date report reviewed
- **Serious adverse event follow-up**
 - Participant ID
 - Date initial event reported
 - Date of event follow-up
 - Event follow-up reported by
 - Event follow-up reported to
 - Time point of event follow-up
 - Date of onset of event
 - Outcome of event (fully recovered / partially recovered / still ongoing / died)
 - Date fully recovered (if applicable)
 - Date partially recovered (if applicable)
 - Date of death (if applicable)
 - Additional actions since initial report
 - Further comments
 - Name of person reporting AE

- Date report completed
- Name of ComBAT team member reviewing the AE
- Date report reviewed
- **Trial Management System**
 - Participant Details
 - Participant ID
 - Site name and site ID
 - Allocation name and allocation ID
 - Date of randomisation
 - Participant Status
 - Participant ID
 - Participant status (e.g. full participation, full withdrawal) and corresponding status ID
 - Details of change
 - Date of change
 - Name of ComBAT team member making the change
 - Participant Forms
 - Participant ID
 - Form name and form ID
 - Stage form was added (e.g. at eligibility, at randomisation)
 - Date form is due
 - Date form is completed by site
 - Date form received by YTU
 - Indicator for switched to postal
 - Form status
 - Details of form status

3.5 Sample Size

The most recent meta-analysis of BA for depression in young people (Martin & Oliver, 2018) reported a large effect size of -0.7 (95% CI -1.20, -0.20). There is no widely accepted minimal important difference (MID) for the RCADS (our primary outcome measure); therefore, we are seeking to obtain an effect size of $d=0.5$, which is accepted (albeit with criticism) as a universal standard for MID (King 2011, Norman et al 2003) and is an effect size which NICE has previously used as a ballpark for the adoption of interventions (NICE, 2014). A sample size of 172 (86 in each group) will have 90% power to detect an effect size of 0.5 on the RCADS using a two-group t-test with a 0.05 two-sided significance level. Assuming an average of 5 participants per therapist, an ICC of 0.01 (DE=1.04) and 23% loss to follow-up (mean of drop-out rates 14-32% from 5 existing RCTs on BA), we will aim to recruit 236 young people (118 in each group).

3.6 Assessment of Eligibility and Randomisation

Potential individuals eligible for participation in ComBAT will be referred by professionals from schools, charities and CAMHS, or self-referred via posters with a contact for their site and/or embedded links to the ComBAT expression of interest form. Trained research assistants within the ComBAT team will conduct screening of the individuals. This includes completing the RCADS depression subscale, the PHQ-9A and determining eligibility based on prespecified inclusion/exclusion criteria specified within the screening CRF in Section 3.4.3. If the young person scores higher than 14 in the PHQ-9A and/or provides answers to the supplementary risk questions, related to suicidal thoughts or attempts, they will be invited to attend a secondary eligibility assessment conducted by a clinical member of the ComBAT

team to confirm if they are eligible. If an individual was deemed eligible, then a research assistant will contact the young person and their parent/guardian to arrange a time to obtain informed consent/assent and conduct a baseline visit. If the clinician felt that the young person's responses indicated more severe depression and complex risk, they would explain that the trial is not suitable for them and provide signposting for further support. The referring site (if applicable) would be informed of this.

Once informed consent/assent is obtained and baseline visit completed, young people will be randomised in a 1:1 ratio to either BA or usual care using simple randomisation. Randomisation will be implemented using a web-based system designed and developed by the data management team at York Trials Unit (YTU). The allocation sequence will be generated by an independent YTU statistician and embedded using a central, web-based randomisation system at YTU.

3.7 Follow-Up

Follow-up will take place 6-months and 12-months post-randomisation.

3.8 Blinding

All research assistants (RAs) collecting data at the 6-month follow-up will be blinded to the participant's treatment allocation. Should any unblinding occur prior to the 6-month follow-up time point, this information will be recorded, and a different RA will be assigned to the participant and will conduct the 6-month follow-up. Participants will be reminded at the start of their follow-up meeting not to give any information that could be used to determine their treatment allocation, such as, what they did during the course of treatment or names of involved therapists.

After all data is collected at the 6-month follow-up, RAs will be unblinded to treatment allocation. This is to aid in the completion of the embedded phenomenological study.

4. Study Data Sources

4.1 Case Report Forms

Case report forms (CRFs) that are received in paper format by York Trials Unit will be scanned by the data management team. Copies of the CRFs annotated with all variable names from the database are to be kept in the YTU analysis directory (Y:\ Project -- comBAT - Statistics).

Data (as detailed above in Section 3.4.3) will be collected from the following CRFs:

- Screening and Eligibility
- Baseline
- Month 6 Follow-up
- Month 12 Follow-up
- Adverse Events
- Serious Adverse Events
- Adverse Events Follow-up
- Serious Adverse Events Follow-up
- Change of Status
- Fidelity Assessment
- Unblinding

4.2 Other Data

4.2.1 Screening Log

Screening data will be collected and inputted by RAs onto Google sheets, updated regularly. The study statistician will clean the screening data in preparation of Programme Management Group and Programme Steering Committee meetings, with any queries being resolved by the ComBAT study team.

4.2.2 Intervention and usual care session logs

Session logs will be completed via Qualtrics using the appropriate Session Record CRF. These will then be reviewed by the ComBAT trial coordinators to remove any identifiable information before sending to the study statistician to be cleaned, with any queries being resolved by the ComBAT study team. The data collected is listed above in Section 3.4.3.

4.2.3 RCADS-25 Qualtrics questionnaire

At both 6 and 12 months, if the research team have been unable to make contact with a participant to arrange a follow-up appointment, a Qualtrics questionnaire containing only the primary outcome (RCADS 25 items) will be sent to the participant. This is to minimize any missing data of the primary outcome measure and ensure that we achieve 90% power as stated in section 3.5 above.

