5.8.2.2 Pattern mixture model

The primary analysis will use a covariance-pattern, repeated-measures, mixed-effect linear regression model, which implicitly assumes missing outcome data are missing at random (MAR). However, it is possible that participants who failed to attend their follow-ups differed from those who did attend (e.g. had worse depression and anxiety symptoms, and therefore would have scored higher on the RCADS-25 if they had attended the follow-up). This would mean the data were missing not at random and would represent a departure from the MAR assumption. The sensitivity of the primary analysis results to departures from the MAR assumption will be explored using a pattern-mixture model, implemented using the `rctmiss`

command (White (2018); White et al (2011). This command currently supports the use of fixed-effect models only, and therefore a linear regression model comparing the primary outcome at 6-months post randomisation will be used, adjusting for treatment arm, age, and sex.

The pattern mixture model works by including a sensitivity parameter quantifying the departure from the MAR assumption. For example, if we expected that those who failed to complete the follow-up at 6-months post randomisation on average would have scored two points lower on the RCADS-25 T-score than those who did attend the follow-up, the sensitivity parameter would be equal to 2. The pattern-mixture model can then be used to obtain an estimate of the treatment effect given this level of departure from the MAR assumption. The `rctmiss` command estimates the treatment effect for varying values of the sensitivity parameter ranging from zero up to any positive value, which allows for the assessment of the impact of varying degrees of departure from the MAR assumption on the treatment effect estimate.

The `rctmiss` command will be used to produce a graph of the adjusted mean difference in RCADS-25 T-scores between treatment groups for varying values of the sensitivity parameter. This will be done assuming the value of the sensitivity parameter is equal in both groups (missing data are equally informative in both groups), and also assuming the sensitivity parameter is equal to zero in the UC group and varying in the BA group, and vice versa (missing data are only informative in one group and not the other).

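### The RCADS-only online form is triggered by failed contact, so as written it does not cover participants who are reached but decline or miss the follow-up appointment

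*SAP*

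**What the plan says.** Section 4.2.3 of the SAP describes a Qualtrics form that carries the 25 RCADS items and nothing else. At 6 and 12 months it is sent "if the research team have been unable to make contact with a participant to arrange a follow-up appointment, a Qualtrics questionnaire" being the means of collection. The reason given is: "This is to minimize any missing data of the primary outcome measure and ensure that we achieve 90% power as stated in section 3.5 above".

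Three other places bear on the point.

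- The Change of Status form in section 3.4.3 distinguishes "Post-randomisation withdrawal (treatment only, follow-up only, full withdrawal"). Someone who has stopped treatment is therefore not, for that reason alone, out of follow-up.
- Section 5.7 assumes missing data are missing at random (MAR) in the primary model. Section 5.8.2.2 then doubts this: "it is possible that participants who failed to attend their follow-ups differed from those who did attend". The doubt is about attendance, not about contact.
- Section 3.5 sets the target: "A sample size of 172 (86 in each group) will have 90% power to detect an effect size of 0.5 on the RCADS", and, with clustering and 23% loss, "we will aim to recruit 236 young people (118 in each group").

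**The concern.** The trigger and the aim do not match. The aim is to lose as few primary outcomes as possible; the trigger picks out one way of losing them. A participant who never answers meets the condition. One who answers and says no to the meeting, or who books and does not turn up while still in contact, does not meet it on a plain reading. The same holds for someone who has withdrawn from treatment only, still owes outcome data, and does not want an appointment.

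What is at stake is avoidable missing data on the intention-to-treat primary endpoint. The pattern-mixture analysis can show how far the result depends on such losses, but it cannot replace an outcome that could have been collected with a form that already exists.

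**Working it through.** **1. The trigger against the ways a follow-up can fail**

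| Situation at 6 or 12 months | Meets the 4.2.3 trigger as written? |
|---|---|
| No contact can be made | Yes |
| Reached, declines the appointment | No |
| Books, does not attend, still in contact | No |
| Withdrawn from treatment only, reached, declines the appointment | No |
| Misses appointments, then goes silent | Arguably yes |

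**2. Do other parts of the SAP fill the gap?**

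- Section 3.4.3 lists a trial-management field recording a switch to post. It gives no rule for when the switch is made.
- Section 5.2.3 allows telephone appointments and online ones without a camera. These are still appointments and do not help with someone who declines one.
- Section 5.8.3 sets no firm deadline for returning data. That tolerates lateness; it does not offer the short form.

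None of these is a rule that offers the RCADS-only form to a participant who is reached but does not attend.

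**3. The SAP's own sample size**

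Inputs from section 3.5: d=0.5, "using a two-group t-test with a 0.05 two-sided significance level", and "Assuming an average of 5 participants per therapist, an ICC of 0.01 (DE=1.04) and 23% loss to follow-up".

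- Two-sample t-test: 85.03 per arm are needed for 90% power; 86 per arm gives 90.3%.
- Design effect: 1 + (5 − 1) × 0.01 = 1.04.
- Inflation: 172 × 1.04 = 178.88; 178.88 / 0.77 = 232.3, so 233, or 234 if rounded within arms.

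The stated 236 is slightly above this and is reproduced.

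**4. Power by loss to follow-up, 236 randomised**

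Effective n per arm = 236 × (1 − loss) / (2 × 1.04).

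| Loss | Effective n per arm | Power |
|---|---|---|
| 14% (lower end of the SAP's quoted range) | 97.6 | 93.5% |
| 20% | 90.8 | 91.8% |
| 23% (planned) | 87.4 | 90.8% |
| 25% | 85.1 | 90.0% |
| 28% | 81.7 | 88.8% |
| 32% (upper end of the quoted range) | 77.2 | 87.0% |

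Power stays at 90% up to about 25% loss, roughly two percentage points above plan.

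**5. What a wider trigger might recover (assumed inputs)**

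At 23% loss, 236 × 0.23 = 54.3 participants are missing. The SAP does not say how many of these would be reached but not attend, or how many of those would complete a short form. If a quarter to a half are of this kind and half of them complete it, the number recovered is 54.3 × 0.25 × 0.5 = 6.8 to 54.3 × 0.5 × 0.5 = 13.6, or about 7 to 14 participants (7/236 = 3.0 to 14/236 = 5.9 percentage points of loss). At 28% loss, recovering three points would bring power back to 90.0%. If few decline, or few who decline would complete the form, the gain is close to nil.

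**The case against.** The strongest reply is that section 4.2.3 sits under study data sources. It tells the analyst where some RCADS values come from and does not set follow-up procedure. How decliners are handled is trial conduct, commonly left to the protocol or working instructions, and the protocol was not available for this review. This has force: those documents may already cover the case, and SAP wording alone cannot change whom the research assistants contact. But the SAP did choose to write a rule with a trigger and a purpose, and on its face the trigger falls short of the purpose.

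Three stronger readings are tempting and are not supported.

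- *That decliners are denied the form and recorded as missing.* The SAP says when the form will be sent. It does not say it is withheld otherwise. The limiting word in 4.2.3 describes the form's content, not its recipients.
- *That power is put at risk.* The 23% is a mean of drop-out rates from earlier trials and may already include people who declined. At that loss, power is above target. The 87.0% belongs to the top of the quoted range and is not tied to decliners.
- *That refusers are the loss most dependent on arm or symptoms, or the people most likely to accept a short form.* Both are plausible, but neither is documented. Section 5.8.2.2 raises the concern for all non-attenders alike, and its analyses let missingness be informative in both arms or in either arm alone.

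**Conclusion.** The point holds as a mismatch between a stated rule and its stated aim. The trigger in section 4.2.3 does not cover participants who are reached but decline or miss the appointment, and no other section supplies a rule that does. The benefit of closing the gap is fewer avoidable missing primary outcomes in a group for which the SAP already doubts MAR. Its size is unknown; the 7 to 14 participants above rest wholly on assumed shares. No shortfall in power has been shown, and nothing here indicates that any participant has been refused the form. It is a cheap improvement and does not undermine the primary analysis.

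**What to change.** Reword section 4.2.3 so that, at 6 and 12 months, the RCADS-25 Qualtrics form goes to uncontactable participants and also to any participant without a completed follow-up who has declined or missed the appointment and has not withdrawn from data collection. Say explicitly that this includes those withdrawn from treatment only. Check the protocol and working instructions: if they already provide for this, a cross-reference is enough; if not, align them, since they govern conduct.

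The cost is a sentence or two, as the questionnaire exists. The one downside is that some participants may prefer the short form to the meeting, which would lose CDRS-R and BADS-SF. Offering it only after the meeting has been declined or missed limits that. The change helps only while follow-up is still under way.
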